13.2 Primary Safety Endpoint and All Secondary Endpoints

The primary safety endpoint will be the rate of sICH together with SADEs (excluding those already counted in sICH), and will be evaluated descriptively and with an unadjusted 95% confidence interval.

Descriptive statistics and unadjusted 95% confidence intervals for secondary endpoints (listed in Section 5.2.3) without any hypothesis tests, will be examined to further advance the safety and efficacy profile of the device.

A summary of the proportions of subjects receiving each category score on the mTICI scale will be reported. Demographics, baseline characteristics, procedural information, and clinical outcomes (efficacy and safety) will also be summarized.

All other binary endpoints will be summarised as proportions with the Wilson exact binomial confidence interval to allow a statement on the uncertainty of the inferred population proportion be made. Descriptive statistics will be used to summarize the clinical outcome variables collected on all vessels treated in this investigation overall and for each center.

The typical value for each continuous response variables will be estimated using the mean and median, while the variability will be estimated using the range, interquartile range and standard deviation. All categorical variables will be reported as counts and percentages.

Box and bean plots will be generated for each continuous response variable, while bar charts will be generated for each categorical variable.

At study completion, summaries of each clinical outcome variable will include corresponding 95% confidence intervals in order to provide an estimate of the corresponding population means, medians and proportions.

13.3 Analysis of Ability to Pool Data across Regions and Investigational Sites

To present the data from this clinical study in a summary form, a comparison of both primary endpoints (safety and efficacy) across sites and across regions will be completed to determine if the generated data can be pooled. Logistic regression models will be fitted for both endpoints with the inclusion of region and study site within region as fixed effects Likelihood ratio tests for the site and region terms in these models will be performed for each endpoint at an alpha level of 0.15 to assess whether outcomes across sites or regions are homogenous. Sites within region with low enrolment may be combined to aid model convergence. If there is evidence for lack of homogeneity, summary statistics by region and/or site within region will be presented for the corresponding endpoint.

13.4 Other Analyses

13.4.1 Analysis of data for the different lengths of device used

An analysis of the primary outcome will be undertaken by comparing the proportions for those who had the procedure done using a 21mm device to those who had the procedure done using a 33mm device, to determine if there is any evidence of a difference from the length of the device used, or if the data are exchangeable between the two device sizes.

13.4.2 Analysis of data for the different versions of device used

The device used under CIP002 rev 03 from the start of the study were of 21 mm length (Product code ET 008 in the US, and ET 007 in Europe). When the protocol was revised from rev 03 to rev 05, new product codes (ET 008-21 and ET 008-33 in the US; ET-007-021 and ET-007-033 in Europe) were introduced. These were for a 21mm length and a 33mm length of device. The revised 21 mm length device was identical to the earlier product except for the addition of two extra radiopaque markers to aid with fluoroscopic visibility. Therefore, the data for all 21 mm length devices is considered completely exchangeable.

Table 5: Device characteristics

Characteristics	Revascularization Device		
	ET-008	ET-008-521	ET-008-533
Indications for Use	The EmboTrap device is intended to restore blood flow in the neurovasculature by removing thrombus in patients experiencing ischemic stroke within 8 hours of symptom onset. Patients who are ineligible for intravenous tissue plasminogen activator (IV t-PA) or who fail IV t-PA therapy are candidates for treatment.	Identical	Identical
Stent Material	Nitinol	Identical	Identical
Stent Diameter	5 mm	Identical	Identical
Stent Working Length	21 mm	Identical	33 mm
Radiopaque Materials	Gold Markers (outer cage) Platinum/Tungsten (proximal/distal coils)	Identical	Identical
Shaft Material	Nitinol Wire with PTFE Coating	Identical	Identical
Shaft Length	190 cm	Identical	Identical
Minimum Microcatheter ID	0.021"	Identical	Identical
Method of Supply	Insertion tool and pre-loaded EmboTrap device are packaged in a protective polypropylene hoop, within a labelled Tyvek pouch and unit carton.	Identical	Identical
Sterilization Method	Ethylene Oxide	Identical	Identical

Below is a summary of the three device types included in the study. For European distribution different codes were used. The devices excluding the packaging are identical.

Table 6: Summary of study devices

Types of Device	United States code	European code	Comparison of the devices U.S. and EU codes
First type 21mm long	ET-008	ET-007	Identical unit except for packaging
21 mm long + marker bands	ET-008-521	ET-007-521	Identical unit except for packaging
33mm long + marker bands	ET-008-533	ET-007-533	Identical unit except for packaging

For the purpose of statistically analysing the devices used the device lot numbers will be extracted from the eCRF database and linked to the size of device used as described in Table 5.

Table 7: Product code per lot number

Device Lot Number recorded in ARISE II EDC	Product Code
15J120AV	ET-007
15K019AV	ET-007
15L068AV	ET-007
15M063AV	ET-007
16A069AV	ET-007
16A074AV	ET-007
16A142AV	ET-007
16B101AV	ET-007
16B147AV	ET-007
16C004AV	ET-007
16C078AV	ET-007
16D132AV	ET-007
16E125AV	ET-007
16E183AV	ET-007
16F064AV	ET-007
16F116AV	ET-007
16G052AV	ET-007-533
16G086AV	ET-007
16H086AV	ET-007
16H140AV	ET-007
16J037AV	ET-007-521
16K074AV	ET-007-521
16J006AV	ET-007-533
16J077AV	ET-007-533
16J100AV	ET-007-533
16J153AV	ET-007-533
16K113AV	ET-007-533
16L054AV	ET-007-533
15G108AV	ET-008
15K151AV	ET-008
16A153AV	ET-008
16D164AV	ET-008
16J036AV	ET-008-521
16K027AV	ET-008-521
16j005av	ET-008-533
16K028AV	ET-008-533
16L094AV	ET-008-533

To assess these assumptions of exchangeability, the proportions of participants reaching successful endpoint by the primary outcome will be compared across three versions of product included in the study.

13.4.3 Analysis of protocol version subjects were enrolled under

Patients were only enrolled and treated under two revisions of the ARISE II study protocol; revision 03 (issued 19th June 2015) and revision 05 (issued 28th June 2016). The differences affecting data analyses in these versions relate to;

- additional length of device added as a choice
- amendment of inclusion criterion #10 and exclusion criterion #15
- revision in the definition of rescue therapy

An extra analysis of the primary outcome will be undertaken to determine if there is any difference between data from subjects enrolled under revision 03 of the protocol and data from those enrolled under revision 05 of the protocol.

14 Safety Analyses

14.1 Adverse Events

Any adverse events which occur during or after the procedure (up to the 90 day follow-up) will be recorded in the database and documented in the Clinical Study Report (CSR). Adverse events will be adjudicated as to the relationship to the EmboTrap device, procedure or the disease state as well to the severity of the event. Subgroup analyses of the points described in the synopsis will be completed.

An AE that occurs after the ICF has been signed and before the treatment with the EmboTrap has started is identified as a pretreatment AE (PTAE). An AE that occurs after treatment using EmboTrap has started will be considered a treatment emergent AE (TEAE).

All AEs will be categorized using the Medical Dictionary for Regulatory Activities (MedDRA) Coding of Adverse Events nomenclature. Standardized nomenclature that will be ascertained includes lowest level and preferred MedDRA terms, MedDRA System Organ Class. Adverse Events will be summarised based on their severity and relationship to the treatment (as defined by the treating site), with the relationship categorised as 1) Definite, 2) Probable/Possible and 3) Unlikely. Unrelated adverse events will not be reported. Separate tables will be used to show 1) all adverse events and 2) serious adverse events.

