12.1 Clinical Events Committee (CEC)

An independent board consisting of stroke neurologists and neurointerventionalists who are not participating in the study will adjudicate serious adverse events in the trial.

The role of the CEC will be to:

- Adjudicate all hemorrhages documented by the Independent Core Laboratory image reviewer as symptomatic or asymptomatic based on the neurological status of the subject.
- Adjudicate all dissections/perforations documented by the Independent Angiographic reviewer as to relationship to the EmboTrap device and/or IA therapy used.
- Adjudicate whether an SAE is deemed attributable to the procedure, to the EmboTrap Device, Adjuvant therapy (IA thrombolysis, thrombectomy), or from the natural course of the initial stroke.
- Continuous evaluation of available external data and/or knowledge, as presented at major congresses and /or published in peer-reviewed journals, which may have an impact on the adjudication and analysis of the reported events.

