5.3 Other important Procedural data

The procedural success rate will be reported as follows:

The **overall procedural success rate** of the study is revascularization measured using modified Thrombolysis in Cerebrovascular Infarction (mTICI inclusive of the 2c rating). Successful achievement of procedural success is defined as achieving a mTICI score of 2b or greater, as assessed by the angiographic core laboratory, in the target vessel prior to the end of the procedure irrespective of the means or number of passes to achieve.

Procedural success using the EmboTrap device alone is the revascularization rate measured using modified Thrombolysis in Cerebrovascular Infarction (mTICI inclusive of the 2c rating). Successful achievement of EmboTrap procedural success is defined as angiographic core laboratory confirmation of a mTICI score of 2b or greater in the target vessel on the last pass of EmboTrap without rescue therapy.

5.4 *Source of Endpoint data and Derived variables*

All endpoint data are taken from the finally monitored data collected through the eCRF or in the case of safety endpoints as adjudicated by Clinical Events Committee and imaging endpoints as adjudicated by the core laboratory.

The primary efficacy endpoint of modified Thrombolysis in Cerebrovascular Infarction (mTICI inclusive of the 2c rating) will be extracted from the data provided by Imaging Core Laboratory Intrinsic imaging following all adjudications being completed in the Imaging consensus section of the eCRF.

Results recorded as TICI 2b, TICI 2c or TICI 3 , following 3 or less passes of the EmboTrap device, and without the use of rescue therapy, prior to taking the assessment angiogram (as defined in CIP002 rev 05) in the patient will be treated as having successfully achieved the primary endpoint. Results recorded as TICI 0, TICI 1 or TICI 2a will be treated as failures to achieve the primary endpoint.

The numerator used to calculate the primary safety endpoint will be calculated by summing the recorded occurrence of Symptomatic Intracerebral haemorrhage (sICH) within 24 hours (-8/+12 hrs) post-procedure, together with any Serious Adverse Device Effects (excluding those already counted in sICH) occurring.

A good clinical outcome will be judged to be an mRS score of ≤2 at 90(+/-14) days (mRS score range 0-6). Any subject recorded as having a score of 0, 1 or 2 at this timepoint will have successfully met the endpoint. Subject scores of 3 – 6 are considered fails.

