14.2 Deaths, withdrawal, and Serious Adverse Events

14.2.1 Serious Adverse Events and Adverse Device Effects

The analysis of Serious Adverse Events (SAEs) and Serious Adverse Device Effects (SADEs) based on the assessment data provided by the Clinical Events Committee will include:

- An overview of the number of SAEs and number of SADEs recorded in the study. Specifically, the number of patients experiencing at least one SAE and/or at least one SADE, along with whether the patient was withdrawn as a result of either the SAE or the SADE. The information will be summarized using counts and percentages
- Summaries of the number of patients experiencing serious adverse events, by preferred term (counts and percentages)

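### SAP 14.1 tabulates SAEs by one undefined, site-assigned relationship and omits those called unrelated, so a CEC-confirmed SADE or PRSAE can be missing from the table

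*SAP*

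**What the plan says.** SAP 14.1 first describes an adjudicated relationship with several possible targets: "Adverse events will be adjudicated as to the relationship to the EmboTrap device, procedure or the disease state". It then builds its summaries on a different variable: "Adverse Events will be summarised based on their severity and relationship to the treatment (as defined by the treating site". That variable has three levels, "with the relationship categorised as 1) Definite, 2) Probable/Possible and 3) Unlikely", and the rule covers two displays: "Separate tables will be used to show 1) all adverse events and 2) serious adverse events". The section adds: "Unrelated adverse events will not be reported".

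Elsewhere the source is the CEC. Protocol 12.1 gives the committee this duty: "Adjudicate whether an SAE is deemed attributable to the procedure, to the EmboTrap Device, Adjuvant therapy", with the natural course of the stroke as a further option. SAP 5.2.3 defines both SADE and PRSAE as CEC-confirmed, the first for the device and the second for the interventional procedure. SAP 5.4 takes endpoint data "in the case of safety endpoints as adjudicated by Clinical Events Committee". SAP 14.2.1 presents SAE and SADE counts, and SAEs by preferred term, "based on the assessment data provided by the Clinical Events Committee".

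**The concern.** This is a single-arm study, and SAP 13.2 evaluates safety descriptively. With no control group, the reader relies on attribution to turn event counts into a statement about the device. The 14.1 SAE table is the only display described in the SAP text that grades relationship. Its input is the treating site's rating, although an independent attribution of the same events is planned and is used everywhere else.

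Two weaknesses follow. First, the combination of a site-based rating and the omission of unrelated events means that the site's judgement decides whether an SAE appears in the table at all. Second, a single undefined treatment axis merges what the protocol keeps apart. SADE and PRSAE are separate endpoints, protocol 3.3 permits rescue therapy after the primary endpoint angiogram, and the CEC has its own category for adjuvant therapy. No rule reconciles the 14.1 table with the CEC-based displays.

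**Working it through.** The documents contain no figure to reproduce. The check sets the rules side by side.

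**Inputs.** Source, scale and omission rule of the tables: SAP 14.1. Source and definition of SADE and PRSAE: SAP 5.2.3 and 5.4. CEC attribution categories: protocol 12.1. I read the sentence on unrelated events as referring to the site's rating, because it follows directly on the site-based scale and no other scale is named.

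**What each combination produces for one SAE:**

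| Site rating | CEC attribution | CEC-based count | 14.1 SAE table |
|---|---|---|---|
| Unrelated | Device | SADE | Absent |
| Unrelated | Procedure | PRSAE | Absent |
| Unlikely | Device | SADE | Listed under Unlikely |
| Definite | Natural course of stroke | Neither | Listed under Definite |
| Definite | Procedure, not device | PRSAE, not SADE | Listed under Definite, not separable from device harm |
| Probable/Possible | Adjuvant therapy | Not a SADE | Listed under Probable/Possible, not separable from device harm |

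Nothing in the text excludes any row. Rows 1 and 2 are the mismatch that matters most: the event counts in an endpoint but is absent from the SAE relationship table. Rows 5 and 6 show the single-axis problem, which remains even if the site and the CEC fully agree on what happened. In row 6 the site is assumed to count rescue therapy as part of the treatment, which SAP 14.1 leaves open. Row 3 is not a contradiction, because the SADE definition includes events in which the device's causal role could not be excluded, and a rating of Unlikely does not exclude it.

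**Bound on the missing events.** Let *D* be the number of SAEs that the CEC attributes to device or procedure, and *U* the number of those that the site calls unrelated. The 14.1 SAE table shows *D* − *U* of them, with 0 ≤ *U* ≤ *D*. The documents give neither *D* nor *U*, so the shortfall can be anything from none to all of these events.

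**What 14.2.1 adds.** Its SAE counts come from the CEC, so an SAE missing from 14.1 should still be counted there by preferred term. But 14.2.1 does not break SAEs down by relationship, and it has no procedure attribution. It therefore does not replace the graded table.

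**The case against.** The strongest reply is that the endpoints are already protected. SADE and PRSAE are CEC-confirmed on separate device and procedure axes, the SAE and SADE overview uses CEC data, and no safety hypothesis is tested. That stands: no endpoint estimate changes. It also disposes of a reading that a reader might infer, namely that 14.1 biases the safety endpoint or that the report would otherwise lack any device or procedure attribution. SADE and PRSAE counts supply that attribution. What they do not supply is relationship by event.

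A second reply is that site and CEC results may properly appear side by side when each is labelled, as they are here. That also stands in principle. Site-assessed relationship is legitimate, and for most non-serious events it may be the only rating, since the CEC's stated remit is SAEs, haemorrhages, dissections and perforations. But the displays are not set side by side. No cross-tabulation is planned, and omitting unrelated events hides exactly the disagreements that a comparison should show.

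A reader might also infer that an event counted as a SADE and rated Unlikely by the site is a direct contradiction. It is not, for the reason given under row 3 of the table, and such an event stays visible in 14.1. Nor is blinding the difference between the two sources: in a single-arm study the CEC also knows which device was under study. The difference is independence.

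Finally, the eCRF and the contents of SAP Appendix 2 (the table listing) are not available. Sites may have rated device and procedure separately, and treatment may be shorthand. This limits what can be asked for non-serious events. It does not repair the 14.1 text, which names one axis and one source.

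**Conclusion.** The point holds as a minor inconsistency in the safety tables that is cheap to improve. The 14.1 SAE table uses a single, undefined, site-assigned relationship where an independent, multi-category attribution is available. A CEC-confirmed SADE or PRSAE can therefore be absent from it, and it cannot separate device, procedure and rescue-therapy harm.

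The effect on the primary safety, SADE and PRSAE estimates is nil. The effect on the table depends on how often a site calls unrelated an SAE that the CEC attributes to device or procedure, and the documents give no basis for a figure. If that never happens, no such event is missing, but the single-axis limitation remains.

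The conclusion assumes that the omission of unrelated events follows the site's rating, and that the available text of 14.1 governs the table layout.

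**What to change.** In SAP 14.1:

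- Base the SAE relationship table on the CEC attribution, with separate columns for EmboTrap device, procedure, adjuvant or rescue therapy, and index stroke. State that rescue therapy under protocol 3.3 falls in the CEC's adjuvant category, if that is the intention.
- Include every SAE, whatever the site rating.
- Show the site rating alongside, as a site-by-CEC cross-tabulation of SAEs.
- For non-serious events keep the site rating, state whether treatment means the device or the procedure, and split the two where the eCRF collected both.

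The cost is SAP wording, reprogramming of the SAE table, a smaller change to the all-AE table and one added cross-tabulation. CEC attribution of SAEs is already a protocol duty, so the SAE change needs no new data and alters neither trial conduct nor endpoints. The downside is wider tables and possibly a higher displayed count of related events.

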12.3 Event notification

12.3.1 Adverse Events (AE) and Adverse Device Effects (ADE)

All adverse events and adverse device effects shall be recorded on sponsor-provided adverse event electronic case report forms eCRF. The safety assessments will consist of Adverse Events (AE) from the time the ICF is signed through Day 90 for those patients enrolled, and to discharge or 72 hours for those patients identified as screening failures through angiographic criteria. Adverse events and adverse device effects shall be recorded in the form of a diagnosis, rather than providing the various signs and symptoms for a particular health condition. The investigator or investigator-appointed study personnel will complete these eCRFs. Adverse event eCRFs should be provided to an appointed Neuravi representative (study monitor) for review within 30 days of becoming aware of the event, and within 24 hours of knowledge of device related adverse events. Copies of related records and reports shall be provided to Neuravi upon request. If the Investigator is made aware of any SAEs after Day 90, these should also be reported to Neuravi or its designee provided the SAE is considered related to the investigational device. The site would then provide a completed SAE form within 1 business day and the event will be followed until resolution, or until adequate stabilization is met.

An AE that occurs after the ICF has been signed and before the treatment with the EmboTrap has started is identified as a pretreatment AE (PTAE). This will include AEs occurring in those patients identified as screening failures through the angiographic inclusion or exclusion criteria. An AE that occurs after treatment using EmboTrap has started will be considered a treatment emergent AE (TEAE). All AEs must be recorded and reported accordingly, whether they appear causally related to the interventional procedure, or not. Adverse events will be followed until the outcome is known or until the Investigator feels no further medical follow-up is warranted.

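### SAP 14.1 says unrelated adverse events will not be reported, yet promises a table of all adverse events and CSR documentation of any event to day 90

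*SAP*

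**What the plan says.** SAP 14.1 makes five statements that bear on which AEs reach the report.

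- On coverage, for any AE during or after the procedure, until the 90-day visit, the section says that it "will be recorded in the database and documented in the Clinical Study Report (CSR"), with no limit by relationship.
- On adjudication, it says: "Adverse events will be adjudicated as to the relationship to the EmboTrap device, procedure or the disease state", and also for severity.
- On the summary, AEs are grouped by severity and by "relationship to the treatment (as defined by the treating site"), in three categories: Definite, Probable/Possible and Unlikely.
- On exclusion, it says: "Unrelated adverse events will not be reported".
- On layout, it says: "Separate tables will be used to show 1) all adverse events and 2) serious adverse events".

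Protocol 12.3.1 adds, for recording and notification, that "All AEs must be recorded and reported accordingly, whether they appear causally related to the interventional procedure, or not".

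**The concern.** The exclusion conflicts with what comes before and after it in the same section. A table presented as showing all AEs would not contain those rated unrelated, and events that the section promises to document in the CSR would have no stated place there. Two programmers working from this paragraph could build different tables.

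The choice of who rates relationship makes this more than a matter of wording. The study is open label with a single arm, so the site's causality call is unblinded and no concurrent control rate puts AE frequencies in context. If the exclusion follows that call, it shapes the AE profile that a reader sees. The exposure is mainly among non-serious events, because serious ones are also summarised elsewhere from CEC data.

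**Working it through.** No rate, margin or sample size enters this point, so there is no figure to reproduce. The check sets the statements against each other and then traces each safety output to its source.

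**Step 1: scope of the exclusion.** The sentence stands directly after the three relationship categories and directly before the sentence promising two tables. Nothing limits it to one summary, and 14.1 points to no listing where unrelated AEs would appear. It does not name who decides that an event is unrelated, but the site's rating is the only one used in that summary.

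**Step 2: what happens to an event under each reading.** Take events after the procedure, up to day 90, that are rated unrelated.

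| Event | Literal reading | Milder reading (limits only the by-relationship summary) |
|---|---|---|
| Non-serious AE | In neither 14.1 table | In the all-AE table |
| SAE | Absent from the 14.1 SAE table, still in 14.2.1 | In both |

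Under the literal reading, the all-AE table is incomplete once one such event occurs. The exclusion makes the 14.1 SAE table differ from 14.2.1 only if at least one SAE is rated unrelated. SAP Table 3 (section 10.7) also lists adverse effects as an outcome compared across product codes. It does not say whether the 14.1 exclusion carries over, so that output is possibly affected.

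**Step 3: outputs outside the exclusion.**

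- Primary safety endpoint (SAP 5.2.2 and 5.4): symptomatic intracranial hemorrhage (sICH) plus SADEs, from CEC-adjudicated data.
- SADE and procedure-related SAE endpoints (SAP 5.2.3): CEC-confirmed.
- sICH, day-7 procedure-related mortality, 90-day all-cause mortality, neurological deterioration and new-territory infarction (SAP 5.2.3 and Table 1): each has its own definition, which does not use the site's AE relationship rating.
- Embolization to new territory (SAP Table 1): read by the core laboratory from the angiogram.
- SAE and SADE summaries (SAP 14.2.1): based on CEC data, with all SAEs by preferred term.
- Withdrawals due to AEs (14.2.2) and deaths (14.2.3): no relatedness limit.

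**Step 4: size.** The documents give no AE counts and no share rated unrelated, so the number of omitted events cannot be calculated or bounded.

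**Step 5: availability of the data.** Protocol 12.3.1 requires AEs to be recorded whatever their apparent cause, from consent to day 90 in enrolled patients. The complete table therefore needs no new data.

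**The case against.** The strongest reply is that the sentence limits only the by-relationship summary it follows, and that a table of all AEs, set against a table of serious ones, simply means serious plus non-serious. SAP Appendix 2, the listing of tables and data listings, appears in the supplied text only as a heading, so a complete listing may be planned there. This stands as a possibility, and it means that actual loss of events is not proven. It does not settle the matter, because 14.1 states no such limit.

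A second reply is oversight. Protocol 12.3.1 sends AEs to the CEC and DSMB for periodic review. Protocol 12.1 has the CEC adjudicate SAEs, all hemorrhages documented by the core laboratory, and all dissections and perforations. That narrows the concern for the most device-relevant events, but review by a committee does not put an event in a table.

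Four stronger readings are tempting, and the documents do not support them.

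- A reader might infer that serious events, deaths or the primary safety result could be suppressed. Step 3 shows that they could not.
- A reader might infer a direct breach of protocol 12.3.1. That text sits under event notification and mainly governs eCRF entry and site-to-sponsor reporting, so it shows that the data exist rather than how they must be tabulated.
- A reader might infer that using the site's call contradicts the adjudication statement. The SAP can reasonably use CEC data for safety endpoints and SAEs, and site data for the general AE summary.
- A reader might extend the point to pretreatment AEs and those of angiographic screening failures. The CSR promise covers events during or after the procedure, so they lie outside the contradiction.

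**Conclusion.** The point holds as an internal contradiction in SAP 14.1. Taken literally, the exclusion removes AEs rated unrelated from the two 14.1 tables, and possibly from the product-code comparison in Table 3, against the section's own promises. The consequence falls mainly on non-serious events and cannot be quantified. No primary or secondary safety endpoint, CEC-based summary, withdrawal count or death count changes, so the study's main conclusions are not threatened.

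The conclusion assumes that the sentence means what it says and that the site's rating defines unrelated. Confidence is medium, because the milder reading is open and the contents of Appendix 2 are not in the supplied text. Under either reading, 14.1 needs correction so that it yields one table rather than two possible ones.

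**What to change.** In SAP 14.1:

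1. Delete the exclusion sentence, or limit it expressly to a table of related AEs.
2. Add a fourth relationship category, Unrelated.
3. State that all AEs from the procedure to day 90 are tabulated regardless of relationship, with related AEs as a subset, and that the 14.1 SAE table covers the same events as 14.2.1.

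The cost is a short text revision and longer AE tables. The documents do not say whether the database is locked. SAP 8.2 requires SAP approval before lock, so the text can be corrected if approval is still pending. If not, SAP section 4 allows the fuller tables to be added and identified in the CSR as unplanned.
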